3 STUDY DESIGN

Overview

The trial will be a phase 1a/1b study, randomized, observer-blind, placebo-controlled.

Description of study parts and groups

Phase 1a

Phase 1a of the study will evaluate the safety, tolerability and immunogenicity of a one-dose or two-dose regimen of the VBI-2902a at the low dose level of 5 µg of S protein or placebo in 60 healthy adults 18 to 54 years of age with no previous clinical or laboratory diagnosis of COVID-19 or SARS-CoV-2 infection and not previously received an experimental or authorized COVID-19 vaccine. Participants will be randomized to three cohorts at a 1:1:1 ratio (2:1 ratio to VBI-2902a or placebo [saline]):

- **Group G1** – 20 participants will receive VBI-2902a at a dose of 5 µg of S protein at Day 1 and placebo at Day 28.

- **Group G2** – 20 participants will receive VBI-2902a at a dose of 5 µg of S protein at Days 1 and 28.
- **Group G3** – 20 participants will receive placebo at Days 1 and 28.

An Independent Data Safety Monitoring Board (DSMB) will review blinded safety data (reactogenicity, adverse events and safety laboratory assessments) at Day 7 after the first vaccination. The second vaccination will only be given if the DSMB confirms that Day 7 safety is acceptable and that stopping rules were not met. The DSMB will further review blinded post-vaccination safety through Day 35, 7 days after the second vaccination and through Day 56, 28 days after the second vaccination. A Study Steering Committee (SSC), comprised of representatives from the study sponsor (not involved in study operations) and external vaccine experts, will review unblinded immunogenicity data 7 days and 28 days after the second vaccination. The study will be unblinded following DSMB review of safety data collected through Day 56.

Phase 1b

Phase 1b of the study will evaluate the safety, tolerability and immunogenicity of a one-dose regimen of VBI-2905a at a 5 µg dose level of S protein in healthy adults (18-54 years) who had been previously vaccinated with mRNA vaccines.

The DSMB will perform an early review of blinded post-vaccination safety data at Day 7 (reactogenicity, AEs and safety laboratory assessments). DSMB will review blinded Day 7 safety data after the first 10 participants in groups G4 and G5 (previously vaccinated). Only after the DSMB confirms that safety is acceptable and that stopping rules were not met will the enrollment in the respective study groups continue to its completion.

The SSC will review unblinded immunogenicity data 7 days and 28 days after the first vaccinations (Groups G4 and G5).

A total of 54 healthy adults, age 18-54 years, with no history of clinical or laboratory diagnosis of SARS-CoV-2 infection or COVID-19 illness, will be enrolled in the Phase 1b part of the study. All participants in Phase 1b will have been previously vaccinated with an authorized mRNA COVID-19 vaccine, including the second dose administered at least 4 months prior to enrollment. Participants will be randomized at a 1:1 ratio to receive, in a blinded fashion, one dose of VBI-2905a or placebo:

- **Group G4** – 27 participants who had previously received a full course (2 doses) of an authorized S protein mRNA COVID-19 vaccines, with the second dose administered at least 4 months prior to the enrollment into the study, will receive VBI-2905a at a dose of 5 µg of S protein at Day 1.
- **Group G5** – 27 participants who had previously received a full course of an authorized S protein mRNA COVID-19 vaccines at least 4 months prior to the enrollment into the study, will receive placebo at Day 1.

[figure not shown]
3.1 General Study Design

A study schematic is presented in [Figure 1](#).

Figure 1: Clinical Trial Design

Figure 1: Clinical Trial Design

VBI-2902a / 2905a Phase 1a/1b Study

* Not previously vaccinated with any licensed or experimental COVID-19 vaccine and no history of clinical or laboratory diagnosis of SARS-CoV-2 infection or COVID-19 illness

** Received a full course of an authorized mRNA COVID-19 vaccine at least 4 months prior to the study and no history of clinical or laboratory diagnosis of SARS-CoV-2 infection or COVID-19 illness

3.2 Randomization and Study Treatments

Randomization of subjects will vary based on which phase and part of the study is currently enrolling. Description of the randomization allocations & treatment arms is outlined in the description of the study design above.

3.3 Sample Size and Power

A total of approximately 60 participants will be enrolled in Phase 1a and approximately 54 participants in Phase 1b. Participants in Phase 1a will be randomized at 2:1 to VBI-2902a or placebo. Participants in Phase 1b who have been previously vaccinated with COVID-19 mRNA vaccine will be randomized at 1:1 to receive one dose of VBI-2905a (group G4) or placebo (group G5) at Day 1

The Phase 1a and phase 1b parts of the study are being conducted at clinical sites in Canada. For the Phase 1b part of the study, the sites will only enroll participants who have previously received mRNA COVID-19 vaccines.

With ~10% drop-out rate it is estimated that at least 56 participants will complete Phase 1a and 48 participants will complete Phase 1b. The sample size per active group will allow for the detection of at least a two-fold difference in neutralizing antibody (nAb) titers with 80% power and an alpha error of 0.05.

4 ANALYSIS COHORTS

4.1 All-Enrolled-Cohort (AEC)

The All-Enrolled-Cohort will include all screened participants who provide informed consent and screening or baseline assessments, regardless of the subject's randomization and treatment status in the study.

Summary of analysis of population and disposition will be based on AEC

4.2 Intent-To-Treat Cohort (ITT)

The Intent-To-Treat cohort includes all participants in the AEC who were randomized. Participants will be analyzed as randomized.

Summary of protocol deviations, demographics and baseline characteristics will be based on ITT cohort.

4.3 Safety-Cohort (SC)

The Safety-Cohort will include all participants in the AEC who receive a study vaccination. Participants will be analyzed as vaccinated, i.e., a subject will be assigned according to the vaccination received.

Summary of all safety (AEs, lab, vital sign, physical examination), medical history, prior and concomitant medication will be based on SC.

4.4 Full Analysis Set (FAS)

The FAS will include all participants in the AEC who received at least one dose of the study vaccine and provided at least one evaluable immunogenicity sample both at baseline and after baseline.

Subjects who received a treatment other than that to which they were randomized, but for whom the treatment received can be unequivocally confirmed, will be analyzed as treated, provided they have no other deviations that compromise their data.

Immunogenicity data will be censored (excluded) from immunogenicity analyses at all-time points following the first date of (1) administration of a non-study (licensed) COVID-19 vaccine OR (2) positive SARS-CoV-2 test OR (3) onset of COVID-19 illness

All Immunogenicity analyses will be based on FAS and PPS.

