6.1.12 Sampling Schedule

See [Table 1](#), and [Table 2](#)[Section 4](#) for the schedules of events.

Blood samples for human immunodeficiency virus (HIV), hepatitis B and hepatitis C: approximately 10 mL is taken at the screening visit. A positive test is exclusionary.

Nasal/nasopharyngeal swab for SARS-CoV-2 virus by PCR or rapid antigen test and viral sequencing:

Nasopharyngeal swabs are taken at the screening visit and all subsequent visits. In Phase 1b, two swabs will be taken, one for SARS-CoV-2 virus testing and one to be stored frozen for potential sequencing at a later time point. A positive test at screening is exclusionary. Timepoints are as follows:

- o Phase 1a: Days 1, 7, 28, 35, 56, 112, 224 and 336
- o Phase 1b: Days 1, 7, 14, 28, 56, 84, 168 and 336

Blood samples for hematology/ biochemistry: approximately 6 mL of blood will be taken at the screening visit and all subsequent visits. Timepoints are as follows:

- o Phase 1a: Days 1, 7, 28, 35, 56, 112, 224 and 336
- o Phase 1b: Days 1, 7, 28, 56, 84, 168 and 336

Blood samples for humoral immune responses: approximately 10 mL of blood will be taken at day 1 and all subsequent visits. Timepoints are as follows:

- o Phase 1a: Days 1, 7, 28, 35, 56, 112, 224 and 336
- o Phase 1b: Days 1, 7, 14, 28, 56, 84, 168 and 336

Blood samples for cell-mediated immune responses: approximately 40 mL of blood will be taken at day 1 and all subsequent visits. Timepoints are as follows:

- o Phase 1a: Days 1, 7, 28, 35, 56, 112, 224 and 336
- o Phase 1b: Days 1, 7, 14, 28 and 336

Urine samples for urinalysis: screening and all subsequent visits. Timepoints are as follows:

- o Phase 1a: Screening and Days 1, 7, 28, 35, 56, 112, 224 and 336
- o Phase 1b: Screening and Days 1, 7, 14, 28, 56, 84, 168 and 336

Urine samples for pregnancy test: screening and day of vaccination. Timepoints are as follows:

- o Phase 1a: Screening and Days 1 and 28
- o Phase 1b: Screening and Day 1

The total amount of blood to be drawn for clinical laboratory tests and immunology evaluations is approximately 15-20 mL for screening and subsequent blood draws that do not include blood samples for cell-mediated immune responses and approximately 55-60 mL for subsequent blood draws that do include blood samples for cell-mediated immune responses.

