4.5 Per-Protocol-Cohort (PPC)

The PPC will include all participants in the FAS who:

- met all eligibility criteria
- received all study vaccinations according to the protocol
- have evaluable serum immunogenicity samples at baseline and at the time points of interest
- had no major protocol deviations (PD) leading to exclusion.

Immunogenicity data will be censored (excluded) from immunogenicity analyses at all timepoints following the first date of (1) administration of a non-study (licensed) COVID-19 vaccine OR (2) positive SARS-CoV-2 test OR (3) onset of COVID-19 illness

Immunogenicity data will be censored (excluded) from immunogenicity analyses at all-time points following the first date of (1) administration of a non-study (licensed) COVID-19 vaccine OR (2) positive SARS-CoV-2 test OR (3) onset of COVID-19 illness

All immunogenicity analyses will be based on FAS and PPC.

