6.4 Immunogenicity Analyses

Unblinded Immunogenicity analyses will be provided at day 35 and day 56 analyses

Immunogenicity analysis will censor the immunogenicity measurements first time after the participants receive a licensed (non-study) COVID-19 vaccines or tested positive SARS-CoV-2 infection or develop COVID-19 illness during the study

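### Immunogenicity censoring starts only after the trigger date, so serum drawn at the visit where a routine swab is first positive stays in the FAS and PPC unless illness onset was recorded earlier

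*SAP*

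**What the plan says.** SAP 4.4 removes FAS immunogenicity data "at all-time points following the first date of (1) administration of a non-study (licensed) COVID-19 vaccine OR (2) positive SARS-CoV-2 test". The sentence then adds a third trigger, so that its last two read "positive SARS-CoV-2 test OR (3) onset of COVID-19 illness". SAP 4.5 applies the same rule to the PPC: "at all timepoints following the first date of (1) administration of a non-study (licensed) COVID-19 vaccine OR (2) positive SARS-CoV-2 test". SAP 6.4 repeats it for the analysis as a whole: "Immunogenicity analysis will censor the immunogenicity measurements first time after the participants receive a licensed (non-study) COVID-19 vaccines or tested positive SARS-CoV-2 infection". All three places use *following* or *after*. None says *on or after*, and none deals with a serum drawn on the trigger date itself.

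On collection, Protocol 6.1.12 says of swabs: "Nasopharyngeal swabs are taken at the screening visit and all subsequent visits". Of humoral serum it says: "approximately 10 mL of blood will be taken at day 1 and all subsequent visits". The Phase 1a day list printed under both items is the same: "Phase 1a: Days 1, 7, 28, 35, 56, 112, 224 and 336". In Phase 1b both lists are Days 1, 7, 14, 28, 56, 84, 168 and 336.

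**The concern.** The SAP revision history shows that the rule was added to keep antibody from licensed vaccines or natural infection out of the immunogenicity results. A swab that is positive at a scheduled visit shows infection present on that day. Because the rule begins only after that date, the one serum taken when infection was demonstrated falls outside it.

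If that serum already carries an infection response, it is counted as vaccine response in an active arm or as background in a placebo arm. Day 28 and Day 56 neutralizing titers are the primary determinant of immunogenicity in Protocol 4.4. The G4 versus G5 comparison supports the Phase 1b benchmark in Protocol 4.13. Both days have a swab and a serum.

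**Working it through.** The plan states no figure on this point, so the check applies the rule to the schedule.

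**1. Overlap of swab and serum.** Comparing the day lists in Protocol 6.1.12, swab and humoral serum coincide on 8 of 8 days in each phase, 7 of them after Day 1.

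**2. The rule as written (serum day > earliest trigger day) against *on or after* (serum day ≥ earliest trigger day).** For a first positive swab with no earlier onset:

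| First positive | Phase | Sera removed as written | Also removed by *on or after* |
|---|---|---|---|
| Day 28 | 1a | 35, 56, 112, 224, 336 | 28 |
| Day 28 | 1b | 56, 84, 168, 336 | 28 |
| Day 56 | 1a | 112, 224, 336 | 56 |
| Day 56 | 1b | 84, 168, 336 | 56 |
| Day 336 | both | none | 336 |

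The result does not depend on how the test date is defined. If it is the collection date, it equals the serum date. If it is the result date, it is the same day or later. In neither case does the serum follow it.

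**3. The illness-onset trigger.** For a positive swab on Day 56:
- no onset recorded: Day 56 serum kept;
- onset on Day 56: Day 56 serum kept;
- onset on Day 53: 56 > 53, so the Day 56 serum is already removed.

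The gap is therefore confined to infections first found at a scheduled visit with no onset recorded before it, mainly asymptomatic infections or those with onset that day.

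**4. Unscheduled illness visits.** Protocol 4.3 lists a swab there but no immunogenicity serum. Later scheduled sera are censored under either wording, so these infections are unaffected.

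**5. Size if the retained serum is boosted.** If k of n samples are each raised f-fold, the GMT is multiplied by f^(k/n). The numbers per arm come from the documents: 20 per Phase 1a group (Protocol Table 3), and 48 expected Phase 1b completers over two arms, 48/2 = 24 (SAP 3.3). The values of f and k are assumptions.
- k = 1, f = 10, n = 24: 10^(1/24) = 1.10
- k = 1, f = 10, n = 20: 10^(1/20) = 1.12
- k = 1, f = 4, n = 24: 4^(1/24) = 1.06
- k = 1, f = 30, n = 24: 30^(1/24) = 1.15
- k = 2, f = 10, n = 24: 10^(2/24) = 1.21
- k = 3, f = 30, n = 24: 30^(3/24) = 1.53

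The unadjusted fold rise over baseline changes by the same factor, because the baseline titer is untouched.

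**The case against.** The strongest reply is that the rule already catches most of what matters. Participants must report symptoms at once, the onset date is a trigger in its own right, and the illness visit draws no immunogenicity serum. That stands, and it is why the point is limited to visit-detected infections without an earlier onset.

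A reader might infer three stronger things that the documents do not support.

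- *The retained serum is contaminated by construction.* The rule keeps the sample by construction, but a positive swab shows virus on that day, not that antibody has risen. The documents give no time from infection to swab positivity or to antibody rise.
- *Infection may precede detection by weeks because visits are far apart.* Spacing gives the time since the last scheduled swab, not the age of an infection when its swab is positive. The longest gaps also come late: 112 days before Days 224 and 336 in Phase 1a, and 168 days before Day 336 in Phase 1b. Up to the Day 56 decision point, gaps are at most 21 days in Phase 1a and 28 days in Phase 1b.
- *The licensed-vaccine trigger has the same flaw.* Nothing in the documents suggests that a serum drawn on the day of a licensed vaccination would already reflect it.

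Partial safeguards exist. Protocol 7.17 allows elimination from the PPC for a condition that can alter the immune response, but this is discretionary and does not reach the FAS. SAP 6.3.2.5 summarizes SARS-CoV-2 results by time point and SAP 5.1 lists all CRF data, so affected visits could be identified, but neither removes a sample. Protocol 10.3 calls the immunogenicity results exploratory, which lowers the stakes without settling the wording.

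**Conclusion.** The point holds in its limited form. Read literally, SAP 4.4, 4.5 and 6.4 keep the serum from a scheduled visit whose swab is first positive, in both the FAS and the PPC, when no earlier illness onset is recorded.

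A boosted retained sample can only raise its own arm's GMT and fold rise at that visit. The between-arm contrast can go either way: wider if the sample is in the active arm, narrower if it is in placebo. One sample assumed to be raised 10-fold gives 10% among 24 or 12% among 20. This is small beside the two-fold difference in SAP 3.3 and the four-fold benchmark in Protocol 4.13. These sizes assume that the full rise is present on the day of detection. The documents give neither the fold rise nor the number of such infections, so the effect could also be nil. Severity is low; this is a cheap improvement.

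**What to change.** In SAP 4.4, in both copies of the sentence in SAP 4.5, and in SAP 6.4, exclude immunogenicity samples collected on or after the collection date of the first positive swab or the date of illness onset, whichever is earlier. Naming the collection date also settles whether the swab date or the result date counts. Leave the licensed-vaccine trigger as written.

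The cost is a change of wording and at most one additional serum per participant first positive at a visit. Some of the sera lost may not yet have been boosted. If the sponsor prefers to keep same-day sera, the SAP should say so and run the *on or after* version as a sensitivity analysis.

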4.5 Per-Protocol-Cohort (PPC)

The PPC will include all participants in the FAS who:

- met all eligibility criteria
- received all study vaccinations according to the protocol
- have evaluable serum immunogenicity samples at baseline and at the time points of interest
- had no major protocol deviations (PD) leading to exclusion.

Immunogenicity data will be censored (excluded) from immunogenicity analyses at all timepoints following the first date of (1) administration of a non-study (licensed) COVID-19 vaccine OR (2) positive SARS-CoV-2 test OR (3) onset of COVID-19 illness

Immunogenicity data will be censored (excluded) from immunogenicity analyses at all-time points following the first date of (1) administration of a non-study (licensed) COVID-19 vaccine OR (2) positive SARS-CoV-2 test OR (3) onset of COVID-19 illness

All immunogenicity analyses will be based on FAS and PPC.

5 STATISTICAL CONSIDERATIONS AND ANALYSIS

5.1 General Guidance on Data Presentation

Unless otherwise specified, continuous variables will be summarized using descriptive statistics, including n, mean, standard deviation (SD), median, Q1 (1st Quartile), Q3 (3rd Quartile), min and max. Count variables will be summarized using frequency and percentage.

Min and max will have same decimal place as raw data; mean, median, Q1, and Q3 will have one additional decimal place; SD will have two additional decimal places. Percentage, and CV (Coefficient of Variation) (if presented), will be rounded to one decimal place.

For all statistical analyses, unless explicitly stated otherwise, percentages will utilize a denominator corresponding to the number of subjects within each treatment groups.

All summary tables will be presented by treatment groups. Listings will be presented to for all data collected in the CRF.

Generally, the DSMB outputs will be presented using actual treatment for the SC and will summarize the date from each study phase and treatment group separately. The DSMB will review blinded safety data and displays (reactogenicity, AEs and safety laboratory assessments) for treatment/age groupings within phases 1a and 1b. That being said, if deemed necessary, individual subjects may be unblinded per DSMB request. During Phase 1b of the study, the DSMB will review unblinded safety data and displays (reactogenicity, AEs and safety laboratory assessments). Details are outlined in the DSMB SAP.

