4.2 COVID-19 Surveillance

Surveillance for COVID-19 symptoms will be conducted throughout the study. If a participant experiences any of the symptoms listed below, he or she is instructed to contact the study site immediately and participate in an in-person or telehealth visit as soon as possible, optimally within 3 days of symptom onset (and at the latest 4 days after symptom resolution). To confirm the diagnosis, SARS-CoV-2 test (PCR/ or rapid antigen test) should be performed as soon as possible. Participants who test positive for COVID-19 will be discontinued from further vaccination. During the 7 days following each vaccination, potential COVID-19 symptoms that overlap with solicited systemic events (i.e., fever, chills, new or increased muscle pain, diarrhea, vomiting) should not trigger a potential COVID-19 illness visit unless, in the investigator's opinion, the clinical picture is more indicative of a possible COVID-19 illness than vaccine reactogenicity.

Participants will be provided diary cards to record any symptoms.

In Phase 1b, nasopharyngeal swabs samples for SARS-CoV-2 testing will be collected in duplicate with one sample to be used for the PCR/ or rapid antigen test and the second sample stored (frozen) for possible sequencing of viral RNA if SARS-CoV-2 virus is detected.

Clinical Criteria for COVID-19 (CDC - COVID-19 Interim Case Definition, Aug. 5, 2020): In the absence of a more likely diagnosis, at least two of the following symptoms:

- fever (measured or subjective)
- chills
- rigors
- myalgia
- headache
- sore throat
- nausea or vomiting
- diarrhea
- fatigue
- congestion or runny nose

OR

Any one of the following symptoms:

- cough
- shortness of breath
- difficulty breathing
- new olfactory disorder
- new taste disorder

OR

Severe respiratory illness with at least one of the following:

- Clinical or radiographic evidence of pneumonia
- Acute respiratory distress syndrome (ARDS)

4.3 Potential COVID-19 Illness Visit (Optimally Within 3 Days After Onset):

An unscheduled potential COVID-19 illness visit and unscheduled potential COVID-19 convalescent visit are required at any time during the study that COVID-19 is suspected.

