9.2 Study Vaccine Discontinuation

In rare instances, it may be necessary for a participant to permanently discontinue study vaccination. Reasons for vaccine discontinuation may include the following:

- Non-serious AE / SAE
- Positive SARS-CoV-2 (PCR or rapid antigen test)
- Participant request
- Investigator request
- Pregnancy
- Protocol deviation (including no longer meeting all the inclusion criteria, or meeting 1 or more exclusion criteria)
- Other (specify)

Note that discontinuation of study intervention does not represent withdrawal from the study. If study vaccination is permanently discontinued, the participant will remain in the study to be evaluated for safety, immunogenicity, and efficacy.

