2 STUDY OBJECTIVES AND ENDPOINTS

Phase 1a	
Primary Objectives:	Primary Endpoints:
To evaluate the safety and tolerability of VBI-2902a containing 5 µg of S protein in one- or two-dose regimens in previously unvaccinated healthy adults of 18-54 years of age.	
 Rate and severity of local and systemic solicited adverse events (AEs) during 7 days after each study vaccination Rate and severity of unsolicited AEs during 28 days after each study vaccination Rate and severity of medically-attended adverse events (MAAEs) during 28 days after each study vaccination Rate of serious adverse events (SAEs) at during 28 days after each study vaccination AEs leading to discontinuation of study vaccination AEs leading to study discontinuation Rate and severity of laboratory abnormalities (hematology, biochemistry, urinalysis) during 28 days after each study vaccination
Secondary Objective:	Secondary Endpoints: 
 Rate and severity of unsolicited AEs throughout the study Rate and severity of medically-attended adverse events (MAAEs) throughout the study Rate of serious adverse events (SAEs) throughout the study Rate and severity of laboratory abnormalities (hematology, biochemistry, urinalysis) throughout the study GMT and the geometric mean fold increase in serum antibody titer post-vaccination over Day 1 (baseline) at Days 7, 28, 35, 56, 112,

	
224 and 336 (Phase 1a, groups G1, G2 and G3);
 
 ○ Neutralizing activity against spike protein-expressing pseudovirus, and/or PRNT neutralizing activity against wild-type SARS-CoV-2 virus and other variants of concern ○ RBD Antibody titers against wild-type variant spike protein measured by ELISA
Exploratory Objectives	Exploratory Endpoints
Phase 1b	
Primary Objective:	
Endpoints:
 
 • Rate and severity of local and systemic solicited adverse events (AEs) during 7 days after each study vaccination • Rate and severity of unsolicited AEs during 28 days after each study vaccination • Rate and severity of medically-attended adverse events (MAAEs) during 28 days after each study vaccination • Rate of serious adverse events (SAEs) at during 28 days after each study vaccination • AEs leading to discontinuation of study vaccination • AEs leading to study discontinuation • Rate and severity of laboratory abnormalities (hematology, biochemistry, urinalysis) during 28 days after each study vaccination

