6.3.1.2 AE Summaries

An overview summary of TEAEs including:

- 1) Counts and percentages of subjects
 - a. With any TEAE,
 - b. With any local solicited AEs during 7 days of vaccination dosing,
 - c. With any systemic solicited AEs during 7 days of vaccination dosing,
 - d. With any unsolicited AEs within 28 days of each vaccination dose,
 - e. With any unsolicited MAAEs at Day 56 and 28 days after each vaccination dose,
 - f. With any unsolicited SAEs at Day 56 and 28 days after vaccination dose,
 - g. With any unsolicited AEs leading to discontinuation of study vaccination,
 - h. With any unsolicited AEs leading to study discontinuation,
 - i. With any unsolicited AEs during the study,

j. With any unsolicited SAEs during the study.
will be presented stratified by treatment and age group.

For each type of AE noted in the overall summary point 2 except solicited AEs (2b and 2c), we will additionally produce summaries of the AEs by SOC and PT. Furthermore, summaries of event types 2d, and 2i will be presented for by SOC, PT, and severity (mild/moderate/severe/potentially life threatening).

Solicited AEs will be summarized separately for local AEs, systemic AEs, and fever >38 centigrade as collected on the solicited AEs eCRF pages. These summaries will be presented for each dose separately and cumulatively, will count the number of subjects experiencing at least one solicited AE, and will count the number of subjects experiencing at least one of each of the solicited AEs ordered per the solicited AEs eCRF pages.

Lastly, within the solicited AE by SOC/PT summary, 2-sided, alpha=0.05 Fisher's Exact tests will be performed to assess differences in rates of these adverse events between the treatment groups. No adjustment will be made to account for multiplicity of tests performed.

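### In Phase 1a, the default denominator in SAP 5.1 keeps participants who never received dose 2 in the dose-2 solicited AE percentages, which understates those rates

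*SAP*

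**What the plan says.** The first primary endpoint in SAP Section 2 is "Rate and severity of local and systemic solicited adverse events (AEs) during 7 days after each study vaccination".

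SAP 5.1 gives a general denominator that yields only to an explicit statement elsewhere: "percentages will utilize a denominator corresponding to the number of subjects within each treatment groups".

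On solicited events, SAP 6.3.1.2 says: "These summaries will be presented for each dose separately and cumulatively, will count the number of subjects experiencing at least one solicited AE". This defines the numerator. The section gives no denominator for either dose.

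The analysis set in SAP 4.3 needs only one injection: "The Safety-Cohort will include all participants in the AEC who receive a study vaccination". No subset of dose-2 recipients is defined for safety.

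The protocol foresees participants who stop after dose 1. Section 4.2 says: "Participants who test positive for COVID-19 will be discontinued from further vaccination". Section 9.2 adds adverse events, pregnancy, participant or investigator request and protocol deviation as reasons, and Section 10.7 has individual stopping rules. Such participants are still followed: "If study vaccination is permanently discontinued, the participant will remain in the study".

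**The concern.** A reaction rate after an injection has meaning only for people who were given that injection. Under the SAP's default, someone never given dose 2 counts in the dose-2 denominator with no possibility of an event, which is arithmetically the same as being recorded as reaction-free.

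The error has one direction: it can only lower the dose-2 rate. It is largest in the group with the most missed second doses. G2 matters most, because it is the only group that receives active vaccine twice; in G1 and G3 the second injection is placebo. Tolerability of the two-dose regimen is part of the Phase 1a primary objective, and the G2 dose-2 rate is the direct evidence on the second active dose.

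**Working it through.** The documents state no dose-2 rate, so there is no plan figure to reproduce. The check is proportion arithmetic.

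**Inputs**
- Group size N = 20 in each of G1, G2 and G3 (SAP Section 3; for G3, "20 participants will receive placebo at Days 1 and 28").
- k = participants in a group who had dose 1 but not dose 2. The documents give no value; k = 1 to 4 is an assumption.
- x = participants with a solicited event after dose 2; illustrative values.
- A participant stopped after dose 1 is assumed to stay in the assigned group in the safety tables, as nothing in the SAP moves them.

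**Formulas**
- Reported under SAP 5.1: x/N.
- Among dose-2 recipients: x/(N − k).
- Ratio of the two: (N − k)/N = (20 − k)/20, whatever x is (x > 0).

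**Results**

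| k | Factor | x = 9: reported → recipients | x = 10 | x = 14 |
|---|---|---|---|---|
| 0 | 1.00 | 45.0% → 45.0% | 50.0% → 50.0% | 70.0% → 70.0% |
| 1 | 0.95 | 45.0% → 47.4% | 50.0% → 52.6% | 70.0% → 73.7% |
| 2 | 0.90 | 45.0% → 50.0% | 50.0% → 55.6% | 70.0% → 77.8% |
| 3 | 0.85 | 45.0% → 52.9% | 50.0% → 58.8% | 70.0% → 82.4% |
| 4 | 0.80 | 45.0% → 56.3% | 50.0% → 62.5% | 70.0% → 87.5% |

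Each missed second dose lowers the reported rate by 5% in relative terms.

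**Fisher's test.** If the test is run by dose with the same denominators, the two-sided p-value for G2 against G3 depends on the counts:

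| G2 reactors | G3 reactors | Missed in G2 / G3 | p, group denominator | p, recipients |
|---|---|---|---|---|
| 9 | 3 | 2 / 0 | 0.082 | 0.035 |
| 9 | 3 | 2 / 2 | 0.082 | 0.075 |
| 8 | 3 | 2 / 0 | 0.155 | 0.074 |
| 10 | 3 | 2 / 0 | 0.041 | 0.016 |
| 9 | 4 | 2 / 0 | 0.176 | 0.087 |

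Only the first row crosses 0.05.

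**The case against.** The strongest reply is that this affects few tables and may never take effect. Phase 1b is single-dose, so the issue comes down mainly to one cell, G2 after dose 2. Protocol 9.2 describes permanent discontinuation of vaccination as rare. SAP 6.1.1 and 6.2 tabulate vaccinations completed, reasons for stopping and doses received, and SAP 6.3.1.3 lists every solicited event, so a careful reader could recompute the rate. The table shells are in a separate document and may show an N for each dose. All of this stands as a limit on size. None of it overrides the rule in SAP 5.1, and a primary-endpoint percentage should not need recomputing by the reader.

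Four stronger readings are tempting, and the documents do not support them:

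- **That the plan expects about 10% to miss dose 2.** The ~10% in SAP 3.3 is study drop-out, set against study completion. It is not a rate of missed second injections.
- **That the denominator decides significance.** It can, for selected counts, but most rows in the second table do not cross 0.05. SAP 6.3.1.2 places Fisher's test within the solicited AE summary without saying that it is run by dose. The tests are unadjusted, and no stated decision depends on one of them.
- **That a reactogenic first dose could quietly remove many G2 participants.** Dose 2 needs DSMB clearance of the Day 7 data. Two VBI-2902a recipients meeting the stopping criteria halt vaccination pending review. Other reasons, such as a positive test or pregnancy, are not inherently about reactogenicity.
- **That untested participants are counted as SARS-CoV-2 negative.** SAP 6.3.2.5 tabulates positive against negative results, and SAP 5.4 does not impute. The denominator there deserves a clarifying word but does not carry this point.

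**Conclusion.** The point holds for the Phase 1a dose-2 solicited AE percentages. As written, the SAP multiplies them by (20 − k)/20. With k assumed at 1 to 4, the relative understatement is 5% to 20%; at k = 0 it is nil. Dose-1 and cumulative summaries are unaffected by missed second doses, since everyone in the Safety Cohort had a first injection.

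This is more than missing detail: an explicit rule, applied literally, gives the wrong quantity for part of a primary endpoint. It is worth correcting because the direction is known and the correction is cheap, not because a large bias has been shown.

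A reader might infer that the recipients-only percentage is the true dose-2 rate. It is the right rate among those dosed, but those people are partly selected for having tolerated dose 1. Changing the denominator removes the dilution and leaves that selection in place.

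**What to change.** Add a paragraph to SAP 6.3.1.2 stating that:

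- per-dose solicited AE percentages, and any Fisher's test on them, use Safety Cohort participants who received that injection and have solicited data after it;
- AE rates for the 28 days after dose 2 use participants who received dose 2;
- each table shows n/N, with the number not given dose 2 and the reasons alongside, so that selection after dose 1 can be judged;
- Fisher's test is run by dose, cumulatively, or both, whichever is intended.

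The cost is that paragraph and some table programming; data collection and participant procedures do not change. The downsides are that denominators will differ between doses and that dose-2 rates will look slightly less favourable whenever a second dose is missed.
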